16.11 Serious Adverse Event Reporting Requirements

All SAEs must be reported within 24 hours of the site becoming aware of the SAE. Any event that is serious, study drug-related, and unexpected as assessed by the medical monitor or the Sponsor will be submitted to the regulatory authorities in accordance with national regulatory laws and regulations. The PI will be responsible for reporting all SAEs that require reporting to the local or central Institutional Review Board/Ethics Committee (IRB/EC) in accordance with its regulations and guidelines.

16.12 Adverse Event and Serious Adverse Event Follow-up

All AEs and SAEs will be followed up to resolution (the subject's health has returned to her baseline status or all variables have returned to normal) or until an outcome is reached, stabilization occurs (the investigator does not expect any further improvement or worsening of the event) or the event is otherwise explained, regardless of whether the subject is still participating in the study. All appropriate therapeutic measures should be undertaken and recorded. Where appropriate, medical tests and examinations will be performed to document resolution of the event(s).

16.13 Serious Adverse Event Reporting – Procedures for Investigators

Initial Reports and Follow-Up SAE Reports: To report an SAE, the SAE eCRF form within the Electronic Data Capture (EDC) system must be completed. All SAEs, whether or not deemed drug-related or expected, must be reported by the investigator or qualified designee within 24 hours of first becoming aware of the event. The investigator/qualified designee will enter the required information regarding the SAE into the appropriate form, which will automatically result in distribution of the information to the appropriate sponsor contact.

If the EDC system is temporarily unavailable (> 24 hours), the event, including the investigator-determined causality to study drug, should be reported via a paper back-up SAE form to PPD Safety Surveillance (contact information, i.e., e-mail or fax will be available on the SAE form).

Upon return of the availability of EDC system, the SAE information must be entered into the EDC system as soon as possible. The SAE form within the EDC system must be updated within 24 hours of knowledge/receipt of SAE follow-up information.

16.14 Procedures for Emergency Unblinding

This is a double-blind study. The Investigator should only be unblinded if it is necessary to determine treatment of emergency. The study personnel responsible for the treatment assignment can provide the information necessary to unblind the investigator (evaluator), in case of an emergency. If the evaluator is unblinded, the reason for unblinding should be documented in the comment page of the eCRF.

17.0 Data Collection, Study Monitoring and Record Management

17.1 Data Collection and Reporting

Data for this study will be collected using eCRFs. The investigator and study site staff will receive training regarding the completion of the eCRF. Visit-specific data should be entered into the eCRF and be ready for review as soon as possible, but no later than 5 days after each visit/time point.

All protocol-required information collected during the study must be entered by the investigator or designated representative in the source documents and eCRF. All data entry, modification or deletion will be recorded indicating the individual subject, original value, the new value, the reason for change, who made the change, and when the change was made. All data changes will be clearly indicated with a means to locate prior values. The investigator will maintain a list of individuals who are authorized to enter or correct data on the eCRFs.

The investigator or designated sub-investigator, following review of the data in the eCRF, will confirm the validity of each subject's data by signing the eCRF.

17.2 Investigator Study Files

The PI is responsible for maintaining all study-related documents in study files. The Sponsor will notify the PI when retention of study files is no longer necessary. The following documents will be kept in the study files or be readily accessible:

- original protocol and all amendments;
- signed agreement or protocol;
- signed and dated study staff roles and responsibilities log;
- copy of the current *curriculum vitae* of the PI and of all sub-investigators;
- IRB/EC membership list and all IRB/EC approvals for the protocol and amendments, informed consent documentation and all updates, advertisements, and written information provided to subjects; all IRB/EC correspondence; documentation that the Investigator's Brochure and subsequent revisions have been submitted to the IRB/EC; documentation that all SAEs and any periodic safety reports have been submitted to the IRB/EC; and annual IRB/EC renewals (as required);
- updated laboratory certification and the laboratory's normal values (covering the entire time interval of the study for all laboratory tests conducted during the study);
- all confirmations of investigational drug receipt, drug accountability logs and drug return records;
- a CD or DVD containing final subject eCRF data;
- all correspondence to or from the Sponsor or its designees;
- blank informed consent form;
- Investigator's Brochure;
- subject screening log;
- subject list (contains subject initials and/or protocol-specific subject number);
- all subjects' original signed informed consents; and,
- monitoring visit log.

17.3 Retention of Records

Essential documents should be retained until at least 2 years after the last approval of a marketing application and until there are no pending or contemplated marketing applications, or at least 2 years have elapsed since the formal discontinuation of the clinical development of the investigational product. These documents should be retained for a longer period, however, if required by the applicable regulatory requirements or by an agreement with the Sponsor.

The Sponsor will inform the PI/institution in writing of the need for record retention and will notify the PI/institution in writing when the trial-related records are no longer needed.

An investigator who withdraws from the responsibility of maintaining study records or wishes to move them to a new location has the obligation to place them in safekeeping and to inform the Sponsor of their location.

18.0 Analytical Plan

All statistical analysis will be performed using SAS® version 9.3 or later, unless otherwise stated. All statistical tests will be two-sided and interpreted at a 5% significance level.

Descriptive statistics (i.e., mean, standard deviation, median, minimum, maximum, etc.) will be provided for all continuous variables; frequencies and percentages will be tabulated for incidence and categorical variables. For parameters measured over time, observed values and changes from baseline will be described for each time point.

The Mycologically Proven Recurrence and Mycological Eradication rates will be described by baseline *Candida* species, when the number of isolates per species allows.

The percentage of subjects with Mycologically Proven Recurrence will be described by number of VVC episodes in the 12 months prior to randomization.

All analyses will be presented by treatment group, as appropriate. Unless otherwise stated, data will be analyzed as is with no imputation. No adjustment for multiplicity will be employed.

A Statistical Analysis Plan (SAP) describing all final statistical analyses in detail will be provided as a separate document. The SAP will be finalized prior to the unblinding of the study treatments for analysis.

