7.2.4 Rationale for the Study Design

This Phase 3 trial is being conducted as a randomized, double-blind, placebo-controlled study. This design is deemed appropriate in consultation with regulatory agencies for this indication, considering that there are no approved therapies to prevent recurrences in subjects with RVVC.

It is expected that the data generated from this study, along with supportive data from studies of ibrexafungerp in acute VVC, will provide substantive evidence of the safety and efficacy of the proposed dosing regimen of ibrexafungerp to seek regulatory approval for the prevention of RVVC.

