9.2 Key Secondary Endpoint

- Efficacy as measured by the percentage of subjects with no Mycologically Proven Recurrence (defined as an episode of VVC with a total composite score ≥ 3 on the VSS Scale and a culture positive for *Candida* spp. that required antifungal treatment) at TOC (Week 24).

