### 3.2.2. Key Secondary Endpoint:

- Efficacy as measured by the percentage of subjects with no Mycologically Proven Recurrence (defined as an episode of VVC with a total composite score  $\geq 3$  on the Vulvovaginal Signs and Symptoms [VSS] Scale and a culture positive for *Candida* spp. that required antifungal treatment) up to Week 24 (TOC).

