#### 4. General Statistical Considerations

Continuous data will be described using descriptive statistics (i.e. n, mean, standard deviation (SD), median, minimum, and maximum). Categorical data will be described using the subject count and percentage in each category. For the summary statistics of all numerical variables unless otherwise specified, minimum and maximum will be displayed to the same level of precision as reported. Mean and median will be displayed to one level of precision greater than the data collected. Standard deviation / standard error will be displayed to two levels of precision greater than the data collected. P-values will be rounded to three decimal places. If a p-value is less than 0.001 it will be reported as “<0.001.” If a p-value is greater than 0.999 it will be reported as “>0.999.” Data will be displayed in all listings sorted by treatment group.

Subjects will be identified in the listings by the subject identification number concatenated with the investigator number.

When count data are presented, the percentage will be suppressed when the count is zero in order to draw attention to the non-zero counts. A row denoted “Missing” will be included in count tabulations where specified on the shells to account for dropouts and missing values. The denominator for all percentages will be the number of subjects in that treatment within the analysis set of interest, unless otherwise specified.

Unless otherwise specified, baseline will be defined as the last non-missing assessment prior to or on the date (and time if appropriate) of the first dose of study drug. Change from baseline is defined as post-baseline value – baseline value.

The study day will be calculated as follows:

If the assessment date occurs on or after the date of the first dose of study drug:

$$\text{Study day} = \text{assessment date} - \text{first dose date} + 1.$$

If the date of interest occurs before the date of the first dose of study drug:

$$\text{Study day} = \text{assessment date} - \text{first dose date}$$

There is no study day 0.

All analyses will be conducted using SAS Version 9.3 or higher. All statistical tests will be two-sided and interpreted at a 5% significance level.

This statistical analysis plan is created for the main study. Regarding the detailed description of the statistical analysis of the nested sub-study, please refer to the [Appendix 4](#).

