The same inferential analysis employing the same methods as for the primary analysis will be performed for the mITT set and PP set to assess clinical success rate up to the Week 24 (TOC). Subjects whose results are missing at Week 24 (TOC) and subjects who withdraw from the study early will be imputed using the imputation rules described in [Section 4.4.1](#). No adjustment of type I error will be performed as these analyses are considered supportive to the primary analysis.

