## 8.2. Secondary Efficacy Endpoints

### 8.2.1. Clinical Response

The same inferential analysis employing the same methods as for the primary analysis will be performed for ITT, mITT, and PP sets to assess below endpoints.

- The percentage of subjects with no Mycologically Proven Recurrence (defined as an episode of VVC with a total composite score  $\geq 3$  on the Vulvovaginal Signs and Symptoms [VSS] Scale and a culture positive for Candida spp. that required antifungal treatment) up to Week 4, Week 8, Week 12, Week 24 (TOC), and Week 36 (end of follow-up [EOFU]);

- The percentage of subjects with no Mycologically Proven, Presumed or Suspected Recurrences up to Week 4, Week 8, Week 12 and Week 36 (EOFU);
- The percentage of subjects with no Mycologically Proven or Presumed Recurrences up to Week 4, Week 8, Week 12, Week 24 (TOC) and Week 36 (EOFU);

For each specified timepoint, any clinical assessment outcomes at or before the specified visit will be counted. The imputation rules described in [Section 4.4.1](#) will be used for the NRI analyses.

Analysis of time to first recurrence (Mycologically Proven, Presumed or Suspected) and time to first Mycologically proven recurrence of VVC through EOFU will use Kaplan-Meier method to estimate the median recurrence time and its 2-sided 95% CIs based on the ITT, mITT, and PP sets. The time to first recurrence (Mycologically Proven, Presumed or Suspected) and time to first Mycologically proven recurrence of VVC is defined as time (days) from first dose of study drug to the first recurrence (Mycologically Proven, Presumed or Suspected) and first Mycologically proven recurrence of VVC, respectively. Subjects who completed the study will be censored at the last visit date if no previously recurrence of VVC experienced. Subjects who discontinued early will be censored at the last available assessment if no previously recurrence of VVC experienced. Subjects who missed any required assessment of potential recurrence will be censored at the last available assessment before the first missed assessment if no previously recurrence of VVC experienced. If there was no post-baseline assessment of potential recurrence, subjects will be censored at the first dose date of study treatment.

Kaplan-Meier curves for time to the first recurrence (Mycologically Proven, Presumed or Suspected) of VVC and time to first Mycologically proven recurrence will be provided by treatment group based on the ITT, mITT, and PP sets.

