#### **11. Changes in the Planned Analysis**

The following have changed from the protocol:

- For the continuous efficacy endpoints except for the absolute number of Mycologically Proven, Presumed or Suspected Recurrences from Baseline (Day 1) to Week 24 (TOC) and Week 36 (EOFU), a Mixed-Effect Model for Repeated Measure (MMRM) analysis model and an analysis of covariance (ANCOVA) model are recommended rather than a two-way ANOVA model. Baseline value will be considered as possible contributor to any observed differences. Additionally, other variables may be considered during blinded data review.
- Add the randomization stratification factor, uncontrolled diabetes mellitus (Yes or No), as justification factor in the efficacy analyses models.

- For efficacy analyses, Country is recommended rather than site to be used as the justification factor.
- In protocol, it stated that the safety and tolerability as measured by AEs, vital signs, treatment discontinuation and safety laboratory tests at TOC (Week 24). The texts “at TOC (Week 24)” is removed since all safety data captured in this study will be taken into account for analysis.
- Intent-to-treat (ITT) Set definition was changed to be “All randomized subjects who signed the consent form and received at least one dose of study drug (ibrexafungerp or placebo).”
- Modified Intent-to-treat (mITT) Set definition was changed to be “All randomized subjects who signed the consent form and received at least one dose of study drug (ibrexafungerp or placebo), who have a confirmed mycological culture for yeast at Screening and a negative culture for yeast at Baseline (Day 1).”
- The number of recurrence episodes will be classified to 4 order categories for analysis rather than 3 categories as mentioned in the protocol. Updated based on client’s request.

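### The key secondary endpoint is tested at 5% with no link to the primary result, so a positive finding would be nominal only; a fixed sequence would give it error control at no cost to the primary

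*Protocol*

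**What the plan says.** Protocol 18.0 (Analytical Plan) puts all tests at a two-sided 5% level and adds: "No adjustment for multiplicity will be employed". SAP section 4 repeats the level: "All statistical tests will be two-sided and interpreted at a 5% significance level".

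Both documents set one secondary endpoint apart from the rest, with its own objective (Protocol 8.2, SAP 2.2) and its own endpoint section (Protocol 9.2, SAP 3.2.2). SAP 8.2.1 then tests it in one list with the other recurrence endpoints, Week 24 standing beside Weeks 4, 8, 12 and 36: "The same inferential analysis employing the same methods as for the primary analysis will be performed for ITT, mITT, and PP sets". No condition on the primary result is attached.

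The SAP's only statement on type I error is in 8.1.1, about repeating the primary analysis in the mITT and PP sets: "No adjustment of type I error will be performed as these analyses are considered supportive to the primary analysis". SAP 11, which opens "The following have changed from the protocol", adds no testing order, gate or alpha split.

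**The concern.** The label and the analysis rule do not match. An endpoint called key, with its own objective, in a trial whose data are meant, with supporting acute-VVC studies, "to seek regulatory approval for the prevention of RVVC", would normally carry a claim of its own. Protocol 7.2.3 adds to that expectation by presenting it as the most certain diagnosis of recurrence. Under the plan as written it has the same inferential status as any other secondary endpoint.

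Two things follow. If the primary succeeds, a significant key secondary can still be reported only as nominal, because no error-control rule covers it. If the primary misses, nothing in the plan stops a positive key secondary from being put forward alone.

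**Working it through.** **The plan's own figure.** Inputs from Protocol 18.1: success 65% and 43%, two-sided 0.05, 90% power, 1:1, Fisher's exact test, about 240 randomized. Exact enumeration at 120 per arm gives power 90.9%. The smallest total that reaches 90% is 228 (114 per arm). The stated size is adequate, and it allots all of the 0.05 to the primary.

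**Ceiling on the two-test error.** If the tests were independent, P(at least one false positive) = 1 − 0.95² = 9.75%. They are positively correlated, so the true figure is lower.

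**Correlation.** The endpoints are nested: a Mycologically Proven Recurrence, or a missing outcome counted as failure, fails both; a Presumed or Suspected Recurrence fails the primary only. With primary failure rate *p* and key secondary failure rate *k*, the correlation is √[*k*(1 − *p*) / (*p*(1 − *k*))].

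- From the documents: placebo failure 1 − 0.43 = 57%; mean failure across arms (35% + 57%)/2 = 46%.
- Assumed, because the documents do not give them: Proven share of recurrences 30, 50, 70 or 95%; missing 0, 10 or 20%, taken as part of the failure total.
- Lowest: *p* = 0.57, no missing, 30% Proven, so *k* = 0.30 × 0.57 = 0.171 and the correlation is √[(0.171 × 0.43)/(0.57 × 0.829)] = 0.39.
- Highest: *p* = 0.46, 20% missing, 95% Proven, so *k* = 0.20 + 0.95 × 0.26 = 0.447 and the correlation is √[(0.447 × 0.54)/(0.46 × 0.553)] = 0.97.

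**Analytic check.** For bivariate normal statistics, 1 − P(|Z₁| < 1.96 and |Z₂| < 1.96) is 9.3% at correlation 0.40, 7.8% at 0.80 and 6.5% at 0.95.

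**Simulation with the SAP's test.** No effect on either endpoint, 120 per arm, CMH over 8 strata (the four countries in SAP 6.1 by uncontrolled diabetes yes/no), assumed per-arm sizes 68, 4, 15, 1, 15, 1, 15, 1, with 100,000 replicates per scenario:

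| Quantity | Range |
|---|---|
| Primary positive | 4.7-5.1% |
| Key secondary positive, primary not | 1.0-4.3% |
| At least one positive | 5.7-9.3% |

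By Proven share, at least one positive occurs in 8.2-9.3% (30% Proven), 7.3-8.2% (70%) and 5.7-6.3% (95%). The spread within each share comes from the failure and missing rates. An unstratified run gives 5.6-9.3%. Repeat stratified runs agree, apart from a low end of 5.9%.

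**With a fixed sequence.** The key secondary is tested only after the primary rejects. If the primary null is true, any false claim requires a false rejection of the primary, which has probability of at most 0.05. If only the key secondary null is true, its own 0.05 test is the bound. The two-endpoint error is therefore at most 5%, and primary power stays at 90.9%. A Bonferroni split at 0.025 each would lower it to 85.4%.

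**Price to the key secondary.** The documents give no rates for it. If it had the primary's 65% and 43%, its normal-approximation power would go from 93.3% ungated to about 87-91% gated, for correlations from 0 to 0.9.

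**The case against.** The waiver of adjustment is an open choice, not a slip. The primary claim is fully controlled, and nowhere do the documents say that the key secondary will support a labelling claim. The 5.7-9.3% is the error of a two-test family that the plan never defines. It becomes a false-claim rate only if a lone positive key secondary is claimed, which the plan neither authorizes nor forbids. When the primary is significant, the key secondary's p-value is the same with or without a gate. The inputs that drive the range are assumed.

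Most of this stands as a matter of weight. The more telling error figure is the 1.0-4.3% for a lone positive key secondary, and the ranges are illustrative. A gate also does not give the key secondary known power. None of it removes the gap: the unchanged p-value is exactly why the gate costs so little, and without a stated rule that p-value has no error-controlled standing.

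**Conclusion.** The point holds. Neither document has a testing order, a gate or an alpha split for the key secondary, and the SAP's one type I error statement does not reach it. The primary result is not threatened. The loss is that a positive key secondary stays nominal, with a two-endpoint false-positive chance of about 6-9% instead of at most 5%. The excess over 5% appears in every scenario examined; its size depends on the assumed Proven share, missing rate and stratum sizes. This is an inexpensive improvement that should be made, not a defect that invalidates the trial.

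**What to change.** Add to SAP 4 and 8.2.1, before unblinding, wording to this effect:

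> Clinical Success up to Week 24 (ITT; CMH stratified by Country and uncontrolled diabetes; missing as failure under 4.4.1) is tested at two-sided 0.05. If, and only if, it is significant, absence of Mycologically Proven Recurrence up to Week 24 (ITT; same test and imputation) is tested at two-sided 0.05. All other p-values are nominal.

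List this in SAP 11 as overriding the waiver in Protocol 18.0.

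A gated endpoint needs one definition, so settle its timing in the same edit. SAP 3.2.2 reads "that required antifungal treatment) up to Week 24 (TOC", while Protocol 9.2 reads "that required antifungal treatment) at TOC (Week 24". The SAP's own objective in 2.2 still follows the protocol, and SAP 11 does not list the change. The text above uses the SAP's timing, and the SAP's strata in place of the site adjustment in Protocol 18.6.2. Align SAP 2.2 and add the timing change to SAP 11.

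The cost is one paragraph and two entries in SAP 11. Primary alpha, sample size and power do not change. The key secondary cannot be claimed if the primary misses, and the remaining secondary endpoints stay nominal.
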